#### 4.2.3.2 Management of dermatological AEs

Dermatologic AEs of afatinib include rash, acne, dermatitis acneiform, and dry skin. General recommendations for prophylaxis are summarized in [Table 4.2.3.2: 1](#) and grade-specific treatment recommendations are summarized in [Table 4.2.3.2: 2](#). For dose adjustment of afatinib and erlotinib refer to [Section 4.1.4](#).

Specific interventions should be reassessed at least after 2 weeks or at any worsening of symptoms, in which case the specific intervention should be adjusted and, depending on own clinical experience, early involvement of a dermatologist should be considered. (Adapted from [R11-0826](#)).

**Proprietary confidential information.**

© 2016 Boehringer Ingelheim International GmbH or one or more of its affiliated companies. All rights reserved.

This document may not - in full or in part - be passed on, reproduced, published or otherwise used without prior written permission.

Table 4.2.3.2: 1 General recommendation for prophylaxis while receiving study drug

Personal hygiene	
Use of gentle soaps and shampoos for the body, e.g. pH neutral bath and shower formulations and tepid water.
 
Use of very mild shampoos for hair wash.
 
Only clean and smooth towels are recommended because of potential risk of infection. The skin should be patted dry after a shower, whereas rubbing the skin dry should be avoided.
 
Fine cotton clothes should be worn instead of synthetic material.
 
Shaving has to be done very carefully.
 
Manicure, i.e. cutting of nails, should be done straight across until the nails no longer extend over the fingers or toes. It is recommended that cuticles not be trimmed because this procedure increases the risk of nail bed infections.

Sun protection	
Sunscreen should be applied daily to exposed skin areas regardless of season. Hypoallergenic sunscreen with a high SPF (at least SPF30, PABA free, UVA/UVB protection), preferably broad spectrum containing zinc oxide or titanium dioxide are recommended.
 
Patients should be encouraged to consequently stay out of the sun.
 
Protective clothing for sun protection and wearing a hat should be recommended.

Moisturizer treatment	
It is important to moisturize the skin as soon as therapy is started.
 
Hypoallergenic moisturizing creams, ointments and emollients should be used once daily to smooth the skin and to prevent and alleviate skin dryness.
 
Note: avoid greasy creams (e.g. petrolatum, soft paraffin, mineral oil based) and topical acne medications.

Prevention of paronychia	
Patients should keep their hands dry and out of water if ever possible.
 
They should avoid friction and pressure on the nail fold as well as picking or manipulating the nail.
 
Topical application of petrolatum is recommended around the nails due to its lubricant and smoothing effect on the skin.

Table 4.2.3.2: 2 Grade specific treatment recommendations of skin reactions

Severity (CTCAE Grading)	Description	Specific intervention
ACNEIFORM RASH		
Mild (Grade 1)	Macular or papular eruptions or erythema without associated symptoms	
Consider topical antibiotics, e.g. clindamycin 2% or topical erythromycin 1% cream of metronidazole 0.75% or topical nadifloxacin 1%;
 
Isolated scattered lesion: cream preferred.
 
Multiple scattered areas: lotion preferred.

Moderate (Grade 2)	Macular or papular eruptions with pruritus or other associated symptoms; localized desquamation or other lesions covering <50% of BSA	
Topical treatment as for Grade 1 plus short term topical steroids, e.g. prednicarbate cream 0.02% plus an oral antibiotic (for at least 2 weeks) e.g. Doxycycline 100mg b.i.d. or Minocycline hydrochloride 100mg b.i.d.

Proprietary confidential information.

© 2016 Boehringer Ingelheim International GmbH or one or more of its affiliated companies. All rights reserved.

This document may not - in full or in part - be passed on, reproduced, published or otherwise used without prior written permission.

Table 4.2.3.2: 2(continued) Grade specific treatment recommendations of skin reactions

Severity (CTCAE Grading)	Description	Specific intervention
ACNEIFORM RASH		
Severe (Grade 3)	Severe, generalized erythroderma or macular, papular or vesicular eruption; desquamation covering $\geq$ 50% of BSA; associated with pain, disfigurement, ulceration or desquamation	Topical and systemic treatment as for Grade 2. Consider referral to dermatologist. Consider systemic steroids.
Life threatening (Grade 4)	Generalized exfoliative, ulcerative, or bullous dermatitis	See Grade 3. Systemic steroids are recommended.
EARLY AND LATE XEROTIC SKIN REACTIONS - PRURITUS		
Mild (Grade 1)	Mild or localized	Topical polidocanol cream. Consider oral antihistamines (e.g. diphenhydramine, dimethindene, cetirizine, levocetirizine, desloratidine, fexofenadine or clemastine).
Moderate (Grade 2)	Intense or widespread	See Grade 1 plus oral antihistamines; Consider topical steroids, e.g. topical hydrocortisone.
Severe (Grade 3)	Intense or widespread and interfering with activities of daily living (ADL)	See Grade 2.
XEROSIS (DRY SKIN)		
Mild (Grade 1)	Asymptomatic	Soap-free shower gel and/or bath oil. Avoid alcoholic solutions and soaps. Urea- or glycerin-based moisturizer. In inflammatory lesions consider topical steroids (e.g. hydrocortisone cream).
Moderate (Grade 2)	Symptomatic, not interfering with ADL	See Grade 1. In inflammatory lesions consider topical steroids (e.g. hydrocortisone cream).
Severe (Grade 3)	Symptomatic, interfering with ADL	See Grade 2. Topical steroids of higher potency (e.g. prednicarbate, mometasone furoate) Consider oral antibiotics.

Proprietary confidential information.

© 2016 Boehringer Ingelheim International GmbH or one or more of its affiliated companies. All rights reserved.

This document may not - in full or in part - be passed on, reproduced, published or otherwise used without prior written permission.

Table 4.2.3.2: 2(continued) Grade specific treatment recommendations of skin reactions

FISSURES		
Mild (Grade 1)	Asymptomatic	Petroleum jelly, Vaseline® or Aquaphor for 30 minutes under plastic occlusion every night, followed by application of hydrocolloid dressing; antiseptic baths (e.g. potassium permanganate therapeutic baths, final concentration of 1:10,000, or povidone-iodine baths). Topical application of aqueous silver nitrate solutions to fissures.
Moderate (Grade 2)	Symptomatic, not interfering with ADL	See Grade 1. Consider oral antibiotics.
Severe (Grade 3)	Symptomatic, Interfering with ADL	See Grade 2.

#### 4.2.3.3 Management of mucositis/stomatitis

General and grade specific recommendations are described in Table 4.2.3.3: 1. For dose adjustment refer to [Section 4.1.4](#) and for restrictions on concomitant therapies refer to [Sections 4.2.3](#), [10.5](#) and [10.6](#).

Treatment is supportive and aimed at symptom control. These may include atraumatic cleansing and rinsing with non-alcoholic solutions such as normal saline, diluted salt and baking soda solution (e.g. one-half teaspoonful of salt and one teaspoon of baking soda in one quart of water every four hours); avoidance of agents containing iodine, thyme derivatives and prolonged use of hydrogen peroxide; dietary maneuvers such as promotion of soft, non irritating foods like ice-creams, mashed/cooked vegetables, potatoes and avoidance of spicy, acidic or irritating foods such as peppers, curries, chillies, nuts and alcohol. If the patient is unable to swallow foods or liquids, parenteral fluid and/or nutritional support may be needed. Examples of some of the agents suggested in [Table 4.2.3.3: 1](#) include: topical analgesics – viscous lidocaine 2%; mucosal coating agents - topical kaolin/pectin; oral antacids, maltodextrin, sucralfate; topical antifungals – nystatin suspension. (Adapted from [P11-09424](#))

**Proprietary confidential information.**

© 2016 Boehringer Ingelheim International GmbH or one or more of its affiliated companies. All rights reserved.

This document may not - in full or in part - be passed on, reproduced, published or otherwise used without prior written permission.

Table 4.2.3.3: 1 Grade specific treatment recommendations of study-drug related mucositis/stomatitis

Severity (CTCAE grading)	Description	Treatment recommendations	Intervention concerning afatinib treatment/ dose modification
Mild (Grade 1)	Minimal symptoms; normal diet	Oral rinses with agents such as non-alcoholic mouth wash, normal saline, diluted salt and baking soda solution.	No change.
Moderate (Grade 2)	Symptomatic, but can eat and swallow modified diet	Addition of topical analgesic mouth treatments, topical corticosteroids, antiviral therapy if herpetic infection confirmed, antifungal therapy preferably topical on a case by case basis.	Maintain dose if tolerable; Hold dose if intolerable until recovery to grade $\leq 1$ , then restart at the same dose.
Severe (Grade 3)	Symptomatic and unable to adequately aliment or hydrate orally	Same as for Grade 2; institute additional symptomatic therapy (topical or systemic) as clinically indicated.	Hold dose until recovery to grade $\leq 1$ or baseline, then restart at the reduced dose according to Section 4.1.4.
Life threatening (Grade 4)	Symptoms associated with life-threatening consequences	Same as for Grade 2; institute additional symptomatic therapy (topical or systemic) as clinically indicated.	Hold dose until recovery to grade $\leq 1$ or baseline, then restart at the reduced dose according to Section 4.1.4

### 4.3 TREATMENT COMPLIANCE

The study medication will be given in accordance with the protocol and the instructions of the site investigator.

The appropriate number of study medication for one cycle, or 4 weeks, of treatment will be provided to patients to be self-administered at home.

Patients will be asked to bring the remaining trial medication at the end of each cycle to the investigator site for a compliance check. The remaining film-coated tablets will be counted by the investigator/site staff and recorded at the investigator site. Discrepancies between the number of tablets remaining and the calculated number of tablets the patients should have taken must be documented and explained. At the end of each cycle any remaining medication will be collected. If the patient is eligible for further treatment, a new bottle of study medication must be dispensed.

The investigator and/or the sponsor can withdraw a patient from the study in the event of serious and persistent non-compliance which jeopardizes the patient's safety or render study results for this patient unacceptable. Patients repeatedly missing scheduled on-treatment study visits, unless due to exceptional circumstances, are considered non-compliant. A maximum of 20% of doses of study drug may be missed for other reasons than drug-related AEs. Patients who miss taking study drug more frequently are considered non-compliant. The BI clinical monitor must be contacted and these patients will be discussed.

**Proprietary confidential information.**

© 2016 Boehringer Ingelheim International GmbH or one or more of its affiliated companies. All rights reserved.

This document may not - in full or in part - be passed on, reproduced, published or otherwise used without prior written permission.

Non-compliant patients will be included in the efficacy analysis (as part of all patients randomized) and the safety analysis (as part of all patients treated).

## 5. VARIABLES AND THEIR ASSESSMENT

### 5.1 EFFICACY

#### 5.1.1 Endpoints of efficacy

The primary endpoint of this study is progression-free survival, as determined by RECIST 1.1([R09-0262](#)).

The key secondary endpoint of this trial is:

- Overall survival

Other secondary endpoints of this trial are:

- Objective response (CR, PR) according to RECIST 1.1 (R09-0262)
- Disease control (CR, PR, SD) according to RECIST 1.1 (R09-0262)
- Tumour shrinkage
- Health-related Quality of Life (HRQoL)

#### 5.1.2 Assessment of efficacy

##### 5.1.2.1 Tumour Assessment

Response and progression will be evaluated in this study using Response Evaluation Criteria in Solid Tumours (RECIST) guideline version 1.1(R09-0262). Tumour response will be assessed by investigator for clinical management of the patient and by a retrospective central review. Progression free survival will be defined as time from the date of randomization to the date of progression or to the date of death, whichever occurs first.

Full details of imaging procedures and RECIST 1.1 assessment can be found in [Appendix 10.1](#)

##### 5.1.2.1.1 Central imaging

All image data will be sent to a central imaging unit to obtain an independent blinded confirmation of tumour response assessment based on a uniform interpretation of radiographic image data for all patients enrolled in the trial. Upon receipt, the central imaging unit will log all image data into a tracking system and perform quality control of digitised radiographic images. An independent review of radiographic images including (i) sequential lesion selection and measurement and (ii) incremental radiological response assessment followed by (iii) global review of tumour response or progression will be performed by two blinded (with regard to patient, treatment, and visit) radiologists. In the case of disagreement on the radiological assessment at any timepoint between the two primary reviewers, a third

**Proprietary confidential information.**

© 2016 **Boehringer Ingelheim International GmbH** or one or more of its affiliated companies. All rights reserved.

This document may not - in full or in part - be passed on, reproduced, published or otherwise used without prior written permission.

adjudicating radiologist will select one of the primary reviewer's interpretations for all timepoints. The data will also be reviewed by an oncologist who will provide a final assessment for each patient.

The review of the image data will be performed by independent radiologists, who are not affiliated with the study. All procedures will be done according to the specifications provided in the investigator site file. The purpose of the blinded reading is to independently assess patient response to therapy and disease progression.

Modifications of the conventional RECIST 1.1 lesion measurement criteria will be introduced into the measurement process in an attempt to reduce variability in the measurements for the independent central imaging review.

Eligibility and treatment decisions will be based on the assessment of disease by the investigator. Central imaging will not be used for this purpose and the results of the central imaging review will not be communicated to the investigator.

After approval of Protocol Version 3.0, the independent imaging review will be discontinued and sites will no longer require to send images to the central imaging unit.

## 5.2 SAFETY

### 5.2.1 Endpoints of safety

Safety of afatinib and erlotinib will be evaluated by intensity and incidence of adverse events, graded according to NCI CTCAE version 3.0 ([R04-0474](#)). Safety endpoints include:

- The overall incidence and intensity of adverse events
- Gastrointestinal events (vomiting, nausea, diarrhoea)
- Skin reactions (rash, acne)

Tolerability of afatinib and erlotinib will be assessed based on dosage reduction and discontinuation due to adverse events.

### 5.2.2 Assessment of adverse events

A diagram of the Adverse event/Serious Adverse events reporting requirements is presented in [Appendix 10.7](#).

#### 5.2.2.1 Definitions of adverse events

##### Adverse event

An adverse event (AE) is defined as any untoward medical occurrence, including an exacerbation of a pre-existing condition, in a patient in a clinical investigation who received a pharmaceutical product. The event does not necessarily have to have a causal relationship with this treatment.

### Serious adverse event

A serious adverse event (SAE) is defined as any AE which results in death, is immediately life-threatening, results in persistent or significant disability / incapacity, requires or prolongs patient hospitalisation, is a congenital anomaly / birth defect, or is to be deemed serious for any other reason if it is an important medical event when based upon appropriate medical judgement which may jeopardise the patient and may require medical or surgical intervention to prevent one of the other outcomes listed in the above definitions.

The following hospitalizations are not considered to be serious adverse events (SAEs) because there is no “adverse event” (i.e., there is no untoward medical occurrence) associated with the hospitalization:

- Hospitalizations for respite care
- Planned hospitalizations required by the protocol
- Hospitalization planned prior to informed consent (where the condition requiring the hospitalization has not changed post study drug administration)
- Hospitalization for administration of study drug

### Intensity of adverse event

The intensity of adverse events should be classified and recorded according to the Common Terminology Criteria for Adverse Events (CTCAE) version 3.0 in the eCRF.

### Causal relationship of adverse event

Medical judgment should be used to determine the relationship, considering all relevant factors, including pattern of reaction, temporal relationship, de-challenge or re-challenge, confounding factors such as concomitant medication, concomitant diseases and relevant history. Assessment of causal relationship should be recorded in the case report forms.

Yes: There is a reasonable causal relationship between the investigational product administered and the AE.

No: There is no reasonable causal relationship between the investigational product administered and the AE.

### Worsening of underlying disease or other pre-existing conditions

Worsening of the underlying disease or of other pre-existing conditions will be recorded as an AE in the eCRF.

If progressive disease occurs and is associated with symptoms, the term “Progressive Disease” should not be reported as AE, however, signs and symptoms of progressive disease will be reported as an (S)AE (if applicable). Exception to this: Death due to progressive disease and where no signs or symptoms are available should be reported as “neoplasm progression (grade 5, outcome fatal).”

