### 3.3.4 Removal of patients from therapy or assessments

#### 3.3.4.1 Removal of individual patients

The Investigator or subject themselves may stop study treatment at any time for safety or due to patient personal reasons.

If a patient is entered in violation of inclusion/exclusion criteria, the sponsor will determine the medical risk/benefit on a case-by-case basis and can require such a patient be discontinued from the study treatment.

A patient is to discontinue study medication if the patient:

1. Withdraws consent to further study medication.
2. Has radiologically documented progressive disease ([Section 5.1.2](#)).
3. Becomes pregnant ([Section 5.2.2.2](#)).
4. Is diagnosed with ILD.
5. Has the need for study drug discontinuation due to AEs or for further dose reductions considered necessary but not allowed according to the protocol ([Section 4.1.4](#)).

The sponsor may remove patients from the study after completion of the primary efficacy analysis if the patient has access to study treatment via options included but not limited to an alternative clinical trial, marketed product, an expanded-access program, named patient use program, compassionate use protocol or other means based on local regulation. This may mean a change in packaging and labelling. The cost of any ongoing supply of study medication (afatinib or erlotinib) will be incurred by the sponsor until disease progression occurs. If a patient is removed from the study treatment, an end of treatment and a follow up visit 28 days later will be performed to ensure all adverse events are followed up and then the patient will be considered to have completed the trial.

Patients who withdraw from the trial after randomisation will not be replaced.

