7.8.1 Adverse events

The analyses of adverse events will be descriptive in nature. All analyses of AEs will be based on the number of patients with AEs and NOT on the number of AEs.

Furthermore, for analysis of AE attributes such as duration, severity, etc. multiple AE occurrence data on the CRF, will be collapsed into AE episodes provided that all of the following applies:

- The same MedDRA lowest level term was reported for the occurrences
- The occurrences were time-overlapping or time-adjacent (time-adjacency of 2 occurrences is given if the second occurrence started on the same day or on the day after the end of the first occurrence)

- Treatment did not change between the onset of the occurrences OR treatment changed between the onset of the occurrences, but no deterioration was observed for the later occurrence

AE episodes will be condensed into AE records provided that the episodes were reported with the same term on the respective MedDRA level and that the episodes are assigned to the same treatment. For further details on summarization of AE data, please refer to the guideline 'Handling and summarization of adverse event data for clinical trial reports and integrated summaries'. (7)

The analysis of adverse events will be based on the concept of treatment emergent adverse events (TEAE). That means that all adverse events occurring between first drug intake till 28 days after last drug intake will be assigned to the randomised treatment. All adverse events occurring before first drug intake will be assigned to 'screening' and all adverse events occurring after last drug intake + 28 days will be assigned to 'post-treatment' (for listings only). For details on the treatment definition, see [Section 6.1](#).

An overall summary of adverse events will be presented. This summary will include the first 5 categories from the list below and AEs by highest CTC grade.

The frequency of patients with adverse events will be summarised by highest CTC grade (grade 3, 4, 5 and all grades to allow both treatment groups to fit on one page), treatment, primary system organ class and preferred term. Separate tables will be provided for patients with each of the following AE categories:

- All AEs.
- Drug related AEs.
- AEs leading to dose reduction.
- AEs leading to treatment discontinuation.
- Serious AEs.
- Drug related serious AEs.
- AEs leading to death.
- AEs in Afatinib patients who dose escalate from 40 mg to 50 mg.

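### Protocol 5.2.2.1 leaves it unclear whether symptom-free progression is an AE, and SAP 7.8.1 gives no version of the AE-discontinuation and AE-death tables without progression-related events

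*Protocol*

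**What the plan says.** Protocol 5.2.2.1, under worsening of underlying disease, opens with an unconditional rule: "Worsening of the underlying disease or of other pre-existing conditions will be recorded as an AE in the eCRF". The next sentence begins "If progressive disease occurs and is associated with symptoms, the term" and goes on to say that the term for progression is then not reported, and that its signs and symptoms are reported instead as AEs or SAEs. A third sentence covers fatal cases: "Exception to this: Death due to progressive disease and where no signs or symptoms are available should be reported as" neoplasm progression, grade 5 with fatal outcome. No sentence deals with non-fatal progression without symptoms.

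Protocol 3.3.4.1 lists the reasons for stopping study drug. Reason 2 is "Has radiologically documented progressive disease". Reason 5 begins "Has the need for study drug discontinuation due to AEs", and 3.3.4.1.1 explains it as study drug toxicity. Protocol 5.2.2.2 has the investigator record, for each AE, the action taken with the drug.

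Protocol 5.2.1 defines the tolerability measure: "Tolerability of afatinib and erlotinib will be assessed based on dosage reduction and discontinuation due to adverse events". SAP 7.8.1 lists a table of "AEs leading to treatment discontinuation" and one of AEs leading to death. Both cover all causes. Drug-related versions are listed only for all AEs and for serious AEs.

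**The concern.** A table of AEs leading to discontinuation is normally read as a measure of toxicity. Here progression can reach it by two routes. The first depends on an ambiguity: scan-only progression may be entered as an AE, with drug discontinued as the action taken. The second does not: the signs and symptoms of progression are AEs on any reading, and an investigator may record one of them as the event that stopped drug. Progression deaths reach the fatal-AE table in a similar way.

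Progression is the main component of the primary endpoint, and the trial is designed on the assumption that it comes later on afatinib. To the extent that progression is counted in these tables, an efficacy difference appears as a tolerability difference. Sites that read the paragraph differently could also report differently, and about 200 sites are planned (Protocol 3.3).

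**Working it through.** **1. What the wording gives in each case**

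| Progression | Literal reading of 5.2.2.1 | Reading suggested by the exception sentence |
|---|---|---|
| Non-fatal, scan only | AE, under the general first sentence | Not an AE term |
| Non-fatal, with symptoms | Term not used; signs and symptoms are AEs | Same |
| Fatal, no signs or symptoms available | AE: neoplasm progression, grade 5 | Same |

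The two readings differ only in the first row. The other two rows put progression-related events into the AE data whichever reading is taken.

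**2. Route into the tables**

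AEs count from first dose to 28 days after last dose (Protocol 7.3.3, SAP 7.8.1). All deaths in that window are reportable (Protocol Table 5.2.2.2: 1). Neither Protocol 7.3.3 nor SAP 7.8.1 excludes progression-related terms from the discontinuation table, and SAP 7.8.1 does not exclude them from the death table. Neither ties the discontinuation table to reason 5 of 3.3.4.1.

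**3. Scale of the possible arm difference in AE discontinuations**

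Inputs from the documents: median PFS of 14 weeks (afatinib) and 10 weeks (erlotinib), Protocol 7.6. The ratio 10/14 = 0.714 matches the stated hazard ratio, so exponential PFS is consistent with the design.

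Assumptions, not in the documents:
- p, the share of PFS events that are progressions rather than deaths: 0.7 to 0.9.
- s, the share of progressions coded as an AE with drug discontinued, either directly or through a symptom: 0, or 0.1 to 0.6. It is taken as equal in both arms.
- The design PFS curves stand in for the timing of treatment stops.

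Formulas: proportion with a PFS event by week t is P(t) = 1 - 2^(-t/median). The spurious gap is p × s × [P(erlotinib) - P(afatinib)].

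Week 16: P = 1 - 2^(-16/10) = 67.0% and 1 - 2^(-16/14) = 54.7%, a difference of 12.3 points. With p = 0.8:

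| s | Added, erlotinib | Added, afatinib | Gap |
|---|---|---|---|
| 0 | 0 | 0 | 0 |
| 0.1 | 5.4 | 4.4 | 1.0 |
| 0.3 | 16.1 | 13.1 | 3.0 |
| 0.6 | 32.2 | 26.3 | 5.9 |

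All entries after s are percentage points.

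Range for s of 0.1 or more, over weeks 8 to 24:
- Low end, week 8: P = 42.6% and 32.7%, difference 9.9; 9.9 × 0.7 × 0.1 = 0.7 points.
- High end, week 16: 12.3 × 0.9 × 0.6 = 6.6 points.

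That is roughly 1 to 7 points. With long follow-up nearly all patients have an event and the gap narrows. At week 52, P = 97.3% and 92.4%, difference 4.9; with p = 0.8 and s = 0.1 to 0.6 the gap is 0.4 to 2.4 points.

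No size is given for the death table, because the documents do not say what share of progression deaths falls within 28 days of the last dose.

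**The case against.** A reader might infer that every scan-only progression becomes an AE leading to discontinuation. The documents do not support that. Radiological progression and AEs are separate reasons for stopping, and reason 5 is explained as toxicity. Follow-up also differs by reason: tumour assessments continue unless the patient stopped for progression or pregnancy. Recording one scan under both reasons would cut across this structure, and no text says that a stop for progression is coded as an AE stop. The exception sentence also counts against the literal reading: symptom-free fatal progression would need no exception if symptom-free progression were already an AE term.

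Other points on that side also stand:
- SAP 7.8.1 does plan drug-related tables for all AEs and for serious AEs. Tables are by preferred term, so neoplasm progression would show as its own line.
- For afatinib, dose reduction, the other half of the tolerability measure, is largely protected, because 4.1.4.1.2 ties reductions to drug-related events.
- Reporting instructions also sit in the Investigator Site File and the Appendix 10.7 diagram, which are not visible here and may settle the coding.
- AE analyses are descriptive.

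These points limit the concern but do not remove it. The two tables at issue are the ones without a drug-related version. The discontinuation table is built from AE records, and nothing restricts it to reason 5. The symptom route and the fatal term do not depend on how the ambiguity is resolved. Because the tables are descriptive, no planned sensitivity analysis would reveal the mixing.

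**Conclusion.** The point holds as an ambiguity in the protocol joined to a gap in the SAP tables. Symptom-free, non-fatal progression has no rule of its own, and the tables of AEs leading to discontinuation and to death can combine toxicity with progression.

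The effect on the discontinuation comparison cannot be determined from the documents. It is zero if stops for progression are coded only under reason 2 and no progression symptom is coded as stopping drug. The 1 to 7 point figure, towards the arm with longer PFS, is an illustration. It rests on exponential PFS at the design medians, an assumed 70-90% of PFS events being progressions, and an assumed 10-60% of those being coded as AEs with drug discontinued. It also uses PFS as a stand-in for treatment stops, although primary PFS is centrally reviewed and stops follow the investigator's assessment. The efficacy analyses, type I error and power are not affected.

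**What to change.** In Protocol 5.2.2.1, state that RECIST progression alone, with or without symptoms, is captured as an efficacy event and is not an AE term. Keep the existing fatal neoplasm progression term and the reporting of signs and symptoms.

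In SAP 7.8.1, give the tables of AEs leading to discontinuation and AEs leading to death with and without progression-related events; a second version of the SAE table is optional. This can be done from coded neoplasm-progression terms and the investigator's causality judgement, which is already collected. Causality is an imperfect proxy, since an AE unrelated to drug need not be due to progression. An eCRF flag for events due to disease progression would separate symptoms more cleanly, but it is optional.

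The cost is one clarifying sentence, a second version of two or three existing tables, and a few more pages of output. No stopping rule or efficacy analysis changes.
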